### Version 3.0

- General document improvement, e.g. correction of variable labels and oversights in the previous version
- Information about quality control and unblinding included.
- References to the latest CIP version 7.0, especially the change of the statistical design: According to the original statistical planning, the study was designed as a three-stage adaptive group sequential test procedure according to O'Brian Fleming with survival endpoint, where the inverse normal method is used to combine the separate stage information. This strategy is replaced with a single final analysis of all data after study termination. Information from the latest version of the CDMS considered for the specification of variables derived from raw data.
- Labelling of SAP chapters not relevant for the final analysis.
- Further specification of "major protocol deviations" for the per-protocol analysis.
- More detailed information about the primary endpoint analyses.
- Specification of the variables to be analyzed with respect to the other secondary endpoint "Type of initiated therapies".

# 1. Introduction

## 1.1. Aim

The aim of this document is to provide detailed instructions for the confirmatory interim analyses of the primary endpoint and on all descriptive and inferential statistical analyses for the final Clinical Investigation Report (CIR). Inferential analyses of the primary and secondary endpoint(s) as defined in this document are mandatory to be reported in the final CIR.

## 1.2. General information

The text contains verbatim excerpts from the CIP Version 1.0. Such excerpts are italicized with grey background.

The main aspects and the design of the clinical investigation are presented in chapters 2, 3, and 4.

General statistical procedures are summarized in chapter 5. Those methods are used in case there is no other instruction within this document.

Definitions of the specific dates, e.g. effective randomization and termination are presented in chapter 0.

The analysis sets are defined in chapter 7.

Data for the CONSORT diagram and baseline data are handled in chapters 8 and 9.

The primary endpoint is handled in chapters 10 and 11, and the secondary endpoints are handled in the following chapters. Thereby the following statistical considerations are specified:

- Definition of the analysis set for the following analyzes, e.g. excluding patients without any measured or imputed data for this endpoint.
- Definition of the endpoint(s) to be analyzed including references to the source data, e.g. CRF sheet and item.
- Treatment of missing and spurious data for evaluation of the above endpoint(s).
- Exclusion of particular information from the evaluation of the above endpoint(s) in addition to the exclusion of patients from the analysis set.
- Statistical alternative hypothesis/hypotheses (HA) to analyze the above endpoint(s).
- Statistical tests intended to analyze the above hypothesis/hypotheses.

In case some variables, which are needed to analyze the pre-specified endpoints, are currently not included in the CDMS, they are indicated with yellow background and the Statistical Analysis Plan (SAP) has to be updated before the first interim analysis or the final analysis.

All variables are defined in tables using the following columns:

Data file	Name of a data file exported from the CDMS with one data row per unique identifier (e.g. patient-specific "patient_display_ID_full" or event-specific "record_ID").  A new data file (e.g. "data_SAR") might be generated by merging all relevant data from the original CDMS data files and generating derived variables (e.g. BMI from weight and height or date of first AE episode).
Notes	Information whether data has to be presented with descriptive methods as defined in the following sub-chapter, data for listings, or data needed for generating of derived variables only.
Variable name	Original name of a variable in the CDMS data file or name of a derived variable (indicated with a suffix "_SAR").
Variable label	Original labels from the CDMS data will be used for generating the SAR unless a new label is defined in this document ("NEW"). Labels might be omitted or shortened ("...") if remaining clear.
Variable level	Nominal, ordinal, scale (metric, continuous), or date.
Nominal values	Original values from CDMS data will be used for generating the SAR unless new nominal values are defined in this document ("NEW"). Nominal values might be omitted or shortened ("...") if remaining clear. Nominal values for numeric data this information is not applicable (n.a.).

### 1.3. Data for which quality control is required

A quality control is needed for analyses of all endpoints(s) as defined in the clinical investigation plan (CIP).

### 1.4. Unblinding

In the context of the first interim analysis in March 2020, the DSMB discovered inconsistencies in adverse event reporting and consequently recommended unblinding of limited sponsor personnel to perform further investigations on the matter.

For this reason, all persons responsible for SAP 3.0 were unblinded.

## 2. Objectives

### CIP chapter 7.1.1 Primary objectives

The primary objective of the BIO|GUARD-MI study is to investigate whether the early diagnosis of cardiac arrhythmias, provided by the BioMonitor in connection with remote monitoring, and the consequent treatment of the patient will decrease the risk to experience a MACE in patients with a history of MI, CHA2DS2-VASc-Score  $\geq 4$  in men /  $\geq 5$  in women and LVEF > 35 %.

...

### CIP chapter 7.1.2 Secondary objective: Arrhythmia detection

It will be investigated if the implantation of the ICM leads to a faster detection of an arrhythmia that requires a guideline-recommended therapy than a strategy of conventional follow-up.

### CIP chapter 7.1.3 Other secondary objectives

In parallel to the primary objective and the definition of MACE, all individual MACE components will be evaluated separately and compared between the study groups.

7.1.3.1 All-cause mortality ...

7.1.3.2 Cardiovascular death ...

7.1.3.3 Worsening of the patient status due to heart failure ...

7.1.3.4 Hospitalization resulting from arrhythmia ...

7.1.3.5 Hospitalization resulting from acute coronary syndrome ...

7.1.3.6 Hospitalization or death resulting from stroke ...

7.1.3.7 Major bleeding requiring hospitalization ...

7.1.3.8 Systemic embolism requiring hospitalization ...

7.1.3.9 Arrhythmias ...

7.1.3.10 Type of initiated therapies ...

7.1.3.11 Therapies ...

7.1.3.12 Quality of Life (QoL) ...

## 3. Investigational Device

### CIP chapter 4.1 Summary description of the investigational device and its intended purpose

Investigational device: BioMonitor or CE-approved successor.

The BioMonitor is an ICM used to automatically detect and record episodes of arrhythmia in patients at risk for bradycardia, tachycardia, asystole and AF. The ICM is not intended to deliver any therapy.

The device reports the recorded episodes and the related statistical data via a physician's programmer and telemetrically via BIOTRONIK Home Monitoring.

## 4. Design

### CIP chapter 8.1 General Considerations

*The BIO|GUARD-MI study is a multicenter, prospective, randomized (1:1), controlled, parallel-group, open, international study (including USA) with an event-driven design. The study is operatively divided into 2 phases. In the first phase 640 patients will be enrolled within approximately 2 years after FPI. After 600 patient years of cumulative follow-up have been collected, a blinded analysis will be performed to assess the primary endpoint rate. Based on the assessed rate (see section 11.7), the study will enter the second phase or be discontinued prematurely. This is necessary because it is impossible to obtain solid estimates of the endpoint rates for the included population from the literature. In case of a too low endpoint rate, the study could be expected to fail in its primary objective, even if the BioMonitor group had a much reduced endpoint rate.*

*In the second phase enrollment will continue in the same way, but in more investigational sites than the first phase, and without interception until up to 2900 patients entered the study. The duration of the second study phase is estimated to last 4 years but ultimately is dependent on when the number of needed endpoints for the final analysis is reached. In the second phase US patients will contribute to the study.*

...

### CIP chapter 11.1.1 Group sequential design

*According to the original statistical planning, the study was designed as a three-stage adaptive group sequential test procedure according to O'Brien Fleming with survival endpoint, where the inverse normal method is used to combine the separate stage information. This strategy is replaced with a single final analysis of all data after study termination.*

*The first interim analysis has been performed. The planned second interim analysis will not be done. Due to the O'Brien Fleming design with a very low  $\alpha_1 = 0.00025$  for the first interim analysis, an adjusted significance level for the final analysis  $\alpha_{final} = 0.02476$  will maintain the global 1-sided significance level  $\alpha = 0.025$ .*

[figure not shown]
*CIP chapter 8.4.1. CRFs and Forms*

**Table 2: Overview CRFs and Investigations**

Investigation	Enrollment	Baseline	Implantation	Discharge	Telephone contacts (every 6 months)	Arrhythmia notification form	General notification form	IHF notification form	Termination
Patient informed consent	x								
Verification of in- and exclusion criteria	x								
Patient demographics		x							
NYHA class		x							
Echo parameters		x							
Specification of MI	x								
Medical history/Co-morbidities		x							
Cardiovascular medication				x					
Lab parameters				x					
Randomization result		x							
BioMonitor implantation			x						
BioMonitor interrogation			x						
BioMonitor programming			x						
Adverse events		x	x	x	x	x	x	x	x
Arrhythmia classification						x			
Evaluation of necessity to contact patient						x	x	x	
Patient interview						x	x	x	
Evaluation of necessity of diagnostic procedure						x	x	x	
Telephone follow-up questionnaire					x				
Quality of life questionnaires					x				
Documentation of: - reason for visit - performed examinations, therapies, modifications						x	x	x	
Documentation of: - regular or premature termination - reason for premature termination									x

*CIP chapter 9.1 Overview*

**Table 3: Study Flowchart**

## 5. General Statistical Procedures

### 5.1. Descriptive analyses

#### *CIP chapter 11.1.4 Statistical methods*

*Descriptive analyses: The data are presented using descriptive statistical methods. For metric data sets, the mean values, standard deviation, median, maximum and minimum are stated, if appropriate. Ordinal data are described by the median and interquartile range. For nominal data, absolute numbers and relative frequencies are determined.*

For illustration, see the following standard tables with and without subgroup analyses based on dummy data.

#### Nominal – dichotomous data (example with dummy data)

Variable (N total = 10)	Category	N non-missing	Absolute frequency	Relative frequency [%]
Gender	Female	9	3	33.3
History of atrial fibrillation	Yes	8	4	50.0

Variable (N total = 10)	Category	Group Randomization	N non-missing	Absolute frequency	Relative frequency [%]
Gender	Female	Implant(N group = 4)	4	1	25.0
		Control (N group = 4)	4	2	50.0
		All	9	3	33.3
History of atrial fibrillation	Yes	Implant	4	2	50.0
		Control	4	2	50.0
		All	8	4	50.0

#### Nominal data – more than two categories (example with dummy data)

Variable (N total = 10)	N non-missing	I N(%)	II N(%)	III N(%)	IV N(%)
NYHA class	8	1 (12.5%)	3 (37.5%)	3 (37.5%)	1 (12.5%)

Variable (N total = 10)	Group Randomization	N non-missing	I N(%)	II N(%)	III N(%)	IV N(%)
NYHA Class	Implant (N group = 4)	3	0 (0.0%)	1 (33.3%)	2 (66.7%)	0 (0.0%)
	Control (N group = 4)	4	1 (25.0%)	1 (25.0%)	1 (25.0%)	1 (25.0%)
	All	8	1 (12.5%)	3 (37.5%)	3 (37.5%)	1 (12.5%)

Scale / metric data (example with dummy data)

Variable (N total = 10)	N non- missing	Mean	SD	Min	Lower quartile	Median	Upper quartile	Max
Age [years]	9	56.1	15.9	25.0	50.0	60.0	66.0	77.0
Weight [kg]	8	78.5	13.9	55.0	69.5	78.5	89.0	99.0

Variable (N total = 10)	Group Randomization	N non- missing	Mean	SD	Min	Lower quartile	Median	Upper quartile	Max
Age [years]	Implant (N group = 4)	4	61.8	11.2	50.0	55.0	60.0	68.5	77.0
	Control (N group = 6)	4	50.3	21.5	25.0	32.5	53.0	68.0	70.0
	All	9	56.1	15.9	25.0	50.0	60.0	66.0	77.0
Weight [kg]	Implant	3	85.0	7.0	77.0	77.0	88.0	90.0	90.0
	Control	4	76.0	18.5	55.0	62.5	75.0	89.5	99.0
	All	8	78.5	13.9	55.0	69.5	78.5	89.0	99.0

Ordinal data

Identical tables as for metric data but without mean and SD

## 5.2. Inferential analyses

### CIP chapter 11.1.4 Statistical methods

*Inferential analysis of the primary hypothesis: The inverse normal combination test is used to combine the independent increment to a global test statistic. A one-sided logrank test is performed in the context of a confirmatory analysis of the primary hypothesis at every interim and the final analysis.*

*Explorative multivariable analyses are performed (after the termination of the study, i.e. not after interim analysis) based on the Cox regression model.*

*Inferential analysis: For the inferential analysis of metric, normal-distributed data, a t-test for interindividual of independent groups or a paired t-test for the intraindividual comparison of paired data is performed. In case the normality assumption of the data is either a priori not justified as specified in the SAP or overtly violated (i.e. by a significant Kolmogorov-Smirnov-Lilliefors or Shapiro-Wilk test result) a non-parametric Wilcoxon-Mann-Whitney rank-sum test or a Wilcoxon-signed-rank test is performed, respectively. For the analysis of relative frequencies, Fisher's exact test is used.*

For better comparability of results, a non-parametric Wilcoxon-Mann-Whitney rank-sum test or a Wilcoxon-signed-rank test is performed for all inferential analyses of metric data.

### CIP chapter 11.1.1 Statistical design

*According to the original statistical planning, the study was designed as a three-stage adaptive group sequential test procedure according to O'Brien Fleming with survival endpoint, where the inverse normal method is used to combine the separate stage information. This strategy is replaced with a single final analysis of all data after study termination.*

*The first interim analysis has been performed. The planned second interim analysis will not be done. Due to the O'Brien Fleming design with a very low  $\alpha_1 = 0.00025$  for the first interim analysis, an adjusted significance level for the final analysis  $\alpha_{final} = 0.02476$  will maintain the global 1-sided significance level  $\alpha = 0.025$ .*

As already specified in SAP 2-0, a stratification for the final analysis of the primary hypothesis is performed for the variable `amikind_multi = STEMI/NSTEMI`, which is also used for block randomization.

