### 3 INTRODUCTION

Myocardial Infarction (MI) is the closure of a coronary vessel. It leads to the irreversible necrosis of heart muscle secondary to prolonged ischemia. According to the appearance in the electrocardiogram (ECG) MI can be classified as non-ST segment elevation myocardial infarction (NSTEMI) and ST segment elevation myocardial infarction (STEMI) which generally reflects an acute total coronary occlusion.

Although the treatment of MI has improved over the past decades mainly due to introduction of early reperfusion therapy (lytic or percutaneous coronary intervention), every sixth man and every seventh woman in Europe will die from MI . Patients with STEMI have a higher acute risk, however, long-term follow-up showed that death rates were higher among patients with NSTEMI with a two-fold difference at 4 years . An explanation for this may be that NSTEMI patients more frequently present with concomitant cardiovascular risk factors such as hypertension, obesity, diabetes and higher age .

After MI, the heart adapts to the permanent damage. A generalized autonomic dysfunction results in enhanced automaticity of the myocardium and conduction system and can lead to complications that include cardiac arrhythmias. The necrosed area acts as a substrate for re-entrant circuits and the ongoing coronary artery disease can cause electrolyte imbalances and hypoxia which further contribute to the development of cardiac arrhythmias. Cardiac arrhythmias may result in orthostatic hypotension, increase myocardial oxygen requirements, and predispose the patient to develop additional malignant ventricular arrhythmias. Since arrhythmias are expected to be frequent in MI survivors and contribute to the poor prognosis, it may be reasonable to monitor and treat them aggressively.

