### 7.3 Secondary hypotheses

The objective to show that arrhythmias requiring guideline-recommended therapy will be detected earlier in the BioMonitor group will be formally tested similarly to the primary hypothesis. The HR is defined as the rate of the BioMonitor group divided by the rate of the control group.

H0: Null hypothesis:  $H_0 : HR \leq 1$

which means that monitoring patients of the BioMonitor group will *not* lead to a shorter time to first arrhythmia that requires guideline-recommended therapy, in the BioMonitor group compared to the control group.

HA: Alternative hypothesis:  $H_A : HR > 1$

which means that monitoring patients of the BioMonitor group will lead to a shorter time to first arrhythmia that requires guideline-recommended therapy compared to the control group.

It is expected that there is a  $HR > 1$  for the BioMonitor group. A rejection of the null hypothesis indicates that arrhythmias are detected earlier in the BioMonitor group.

No hypotheses have been pre-defined for the other secondary objectives. Details will be specified in a separate Statistical Analysis Plan (SAP).

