## **8.2 Measures taken to minimize or avoid bias**

### **8.2.1 Randomization**

A block randomization stratified for center effects and STEMI/NSTEMI is used to minimize any potential bias due to center specific effects and STEMI/NSTEMI.

All patients included are assumed to be at increased risk for MACE. However, currently it is unknown which patients benefit particularly from the study treatment. Thus, no other strata are implemented in the randomization procedure.

Due to the large sample size, other unbalanced confounding factors are expected to be of low relevance.

For patients of the BioMonitor group and Control group, the randomization date is defined as the discharge from the index hospitalization.

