### 11.6. Hypotheses & Statistical Tests

#### CIP Chapter 7.2 Primary hypotheses

*For assessing the primary endpoints, Kaplan-Meier curves will be constructed for the time to first MACE for both study groups according to the intention-to-treat principle. The hazard ratio is defined as the rate of the BioMonitor group divided by the rate of the control group.*

*The following set of hypotheses (null hypothesis  $H_0$  and alternative hypothesis  $H_A$ ) will be tested. More detailed information about the endpoints is provided in section 8.3:*

- *$H_0$ : Null hypothesis:  $H_0 : HR \geq 1$  which means that monitoring patients of the BioMonitor group will not lead to a longer time-to-first-event of MACE compared to the control group.*
- *$H_A$ : Alternative hypothesis:  $H_A : HR < 1$  which means that monitoring patients of the BioMonitor group will lead to a longer time-to-first-event of MACE compared to the control group.*

*It is expected that there is a  $HR < 1$  in favour of the BioMonitor group. A rejection of the null hypothesis indicates that the BioMonitor group has a statistically significant longer time to first MACE event compared to the control group.*

The confirmatory analysis of the primary hypothesis is performed according to the methods defined in chapter 0. based on the first primary endpoint after the effective randomization date or censoring at the termination date in the ITT analysis set.

The test of the primary hypothesis is repeated according to the methods defined in chapter 0. based on the first endpoint after the effective randomization date for the PP analysis or censoring at the final date for the final PP analyses in the PP analysis set.

In case the primary alternative hypothesis can be accepted, hazard ratios for the BioMonitor versus control group including 95% CI are additionally calculated based on the Cox regression model for the following conditions:

- ITT analysis set, uncorrected adjudication, stratification amikind\_multi= STEMI/NSTEMI
- ITT analysis set, corrected adjudication, stratification amikind\_multi= STEMI/NSTEMI
- ITT analysis set, corrected adjudication, without stratification
- PP analysis set, corrected adjudication, stratification amikind\_multi= STEMI/NSTEMI
- PP analysis set, corrected adjudication, without stratification

The assumption of proportional hazards is checked graphically by log-minus-log survival versus log-time plots.

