### 12.6. Hypotheses & Statistical Tests

#### CIP Chapter 7.3 Secondary hypotheses

*The objective to show that arrhythmias requiring guideline-recommended therapy will be detected earlier in the BioMonitor group will be formally tested similarly to the primary hypothesis. The HR is defined as the rate of the BioMonitor group divided by the rate of the control group.*

*H0: Null hypothesis:  $H_0 : HR \leq 1$  which means that monitoring patients of the BioMonitor group will not lead to a shorter time to first arrhythmia that requires guideline-recommended therapy, in the BioMonitor group compared to the control group.*

*HA: Alternative hypothesis:  $H_A : HR > 1$  which means that monitoring patients of the BioMonitor group will lead to a shorter time to first arrhythmia that requires guideline-recommended therapy compared to the control group.*

The hazard ratio for the BioMonitor versus control group including 95%CI is calculated with the Cox regression model. In case of doubt about the validity of the Cox model, the assumption of proportional hazards is checked graphically by log-minus-log survival versus log-time plots.

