### 14.6. Hypotheses & Statistical Tests

Differences of the survival curves BioMonitor versus control group are tested for statistical inference with the log-rank test.

The hazard ratio for the BioMonitor versus control group including 95%CI is calculated with the Cox regression model. In case of doubt about the validity of the Cox model, the assumption of proportional hazards is checked graphically by log-minus-log survival versus log-time plots.

## 15. Other sec. EP: Time to 1st worsening of the patient status due to heart failure ...

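### Secondary time-to-event analyses omit the STEMI/NSTEMI stratum used for randomisation and for the primary test; adding it is a small, free improvement

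*SAP*

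**What the plan says.** CIP 8.2.1 gives the allocation scheme: "A block randomization stratified for center effects and STEMI/NSTEMI is used". SAP 5.2 carries one of the two factors into the primary test: "a stratification for the final analysis of the primary hypothesis is performed for the variable" amikind_multi (STEMI/NSTEMI), a choice made in SAP 2.0. SAP 11.6 lists five primary Cox models, some with this stratum and some without, to be calculated only if the primary alternative is accepted. Centre is in none of them. SAP 8.1 uses site only for a count of patients.

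The secondary analyses name no stratum:

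- SAP 14-21 and 23 share one sentence: "Differences of the survival curves BioMonitor versus control group are tested for statistical inference with the log-rank test". A Cox hazard ratio follows.
- SAP 12.6 (time to first arrhythmia detection) and the test section of SAP 13 (death or transplantation) name no log-rank test. SAP 12.6 says: "The hazard ratio for the BioMonitor versus control group including 95%CI is calculated with the Cox regression model".

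For arrhythmia detection, CIP 7.3 says the objective "will be formally tested similarly to the primary hypothesis". The footnote to SAP 9.6 expects no bias in the primary analysis from an MI-type imbalance, because that log-rank test is stratified. Nothing similar is said for the secondary endpoints.

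**The concern.** A factor used to restrict randomisation is normally carried into the analysis. If it is prognostic and left out, the model-based variance does not credit the balance that blocking produced, so the test tends to be conservative. The Cox hazard ratio also becomes a marginal one, somewhat closer to 1 than the within-stratum ratio.

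The protocol gives one figure suggesting that MI type is prognostic. CIP 3 reports that "death rates were higher among patients with NSTEMI with a two-fold difference at 4 years". The death endpoints (SAP 13 and 14) are among those analysed without the stratum. So is arrhythmia detection, the only secondary endpoint with a formal hypothesis.

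At stake is a little precision in a trial that may finish short of its 372 planned events (CIP 11.2), and consistency between the primary and secondary models. No false-positive risk is involved.

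**Working it through.** **Step 1: the plan's own figure.** Inputs from CIP 11.1.1, 11.2 and 11.3: HR 0.7452, one-sided 0.025 overall and 0.02476 at the final analysis, 80% power, 1:1 allocation.

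- Schoenfeld: 4 × (1.960 + 0.842)² / (ln 0.7452)² = 4 × 7.849 / 0.0865 = 363 events. Freedman's formula gives 369. The plan's 372 is reproduced within 3%.
- Power at 372 events: Φ(√372 / 2 × 0.2941 − 1.964) = Φ(0.872) = 80.8%.

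**Step 2: simulation of the strata.**

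- From the documents: up to 2,900 patients, up to 80 sites (CIP Appendix A), drop-out of 5% per year, HR 0.7452, one-sided 0.02476.
- Assumed: NSTEMI hazard twice that of STEMI, 50:50 MI-type split, blocks of 4, unequal centre sizes, follow-up 0.5-6 years, an alternative N of 800, and between-centre SD of log hazard 0, 0.3, 0.5 or 0.8. The documents give no between-centre spread.
- 1,500 trials per scenario. Cells show HR / model SE of log HR / rejection rate.

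| N, events, centre SD | No stratum | MI type | Centre × MI type |
|---|---|---|---|
| 2,900, 377, 0 | 0.7435 / 0.1042 / 81.9% | 0.7415 / 0.1043 / 82.3% | 0.7414 / 0.1077 / 81.2% |
| 2,900, 368, 0.3 | 0.7468 / 0.1055 / 79.9% | 0.7446 / 0.1055 / 80.2% | 0.7417 / 0.1090 / 79.6% |
| 2,900, 371, 0.5 | 0.7538 / 0.1051 / 76.5% | 0.7519 / 0.1052 / 77.4% | 0.7461 / 0.1088 / 76.8% |
| 2,900, 367, 0.8 | 0.7602 / 0.1059 / 73.1% | 0.7584 / 0.1059 / 73.9% | 0.7448 / 0.1098 / 76.8% |
| 800, 371, 0.5 | 0.7687 / 0.1045 / 72.7% | 0.7617 / 0.1047 / 73.5% | 0.7426 / 0.1207 / 68.5% |
| 800, 372, 0.8 | 0.7888 / 0.1043 / 63.8% | 0.7845 / 0.1045 / 66.5% | 0.7449 / 0.1212 / 68.3% |
| 800, 155, 0.5 | 0.7538 / 0.1628 / 40.3% | 0.7510 / 0.1629 / 41.6% | 0.7408 / 0.1836 / 38.5% |

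Under HR = 1, in the same column order, rejection was 2.2%, 2.3%, 2.3% (N = 2,900, SD 0.5) and 1.4%, 1.5%, 1.9% (N = 800, SD 0.8), against 2.476%.

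**Step 3: what the MI-type stratum does.**

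- Power changes by 0.4, 0.3, 0.9, 0.8, 0.8, 2.7 and 1.3 points, in table order.
- The HR moves by 0.002 to 0.007.
- The SE without the stratum is never larger. The biggest difference is 0.0002.
- The larger attenuation in the table (to 0.76-0.79) comes mainly from centre, not MI type. So does the conservatism: at N = 800 and SD 0.8 the unstratified model SE is 0.1043 against a sampling SD of 0.0920, and with MI type it is 0.1045 against 0.0933.
- Monte Carlo error of one rate near 75% is √(0.75 × 0.25 / 1,500) = 1.1 points. Both analyses use the same simulated trials, so their difference is less noisy, but gains below 1 point should not be read as exact.

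**Step 4: a second simulation with country strata.** Assumed 1,600 patients, 70 centres in 12 countries, about 220-260 events, 1,000 trials per cell.

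- None to MI type: 61.3% to 61.2% at SD 0.5, and 50.8% to 51.3% at SD 0.9. At SD 0.9 the HR went from 0.764 to 0.763.
- MI type to country × MI type: 61.2% to 61.1% at SD 0.5, and 51.3% to 54.0% at SD 0.9. An SD of 0.9 implies a 95% range of centre hazards of exp(2 × 1.96 × 0.9), about 34-fold.

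**The case against.** The case for leaving the plan alone is fair on several points.

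- **The endpoints are mostly exploratory.** CIP 8.3.3 disclaims power for them and sets no hypotheses, and MI type is already a predefined subgroup (CIP 11.9). This stands, except for arrhythmia detection, which has a formal hypothesis.
- **CIP 7.3 might already imply the stratum**, by having arrhythmia detection tested like the primary. But the CIP does not mention stratified testing even for the primary. The stratum comes from the SAP, and SAP 12.6 does not repeat it.
- **The two-fold figure is stretched.** It concerns deaths in MI patients generally. CIP 3 suggests it may reflect hypertension, obesity, diabetes and age, and most of these feed the entry score. Two-fold is therefore probably too high here. This stands and shrinks the gain.
- **Attenuation reflects a different estimand, not an error.** This also stands.
- **The change comes late.** SAP 1.4 says everyone responsible for SAP 3.0 was unblinded. This argues against new modelling choices, but less against a factor already fixed for the primary in SAP 2.0.

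A reader might also infer more than the documents support:

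- *That the intervals are wider without strata.* The table shows equal or smaller standard errors.
- *That centre must be added.* Full centre × MI-type strata can lose power (72.7% to 68.5%), and country strata help only under a large assumed spread.
- *That the adverse event reporting inconsistencies in SAP 1.4 were between sites.* The SAP does not say so.
- *That primary and component hazard ratios cannot be compared.* SAP 11.6 lists "ITT analysis set, corrected adjudication, without stratification", though only if the primary succeeds.

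**Conclusion.** The mismatch is real and the consequence small. SAP 12-21 and 23 omit a factor that was used in randomisation and is used in the primary test, including for the one secondary endpoint with a formal hypothesis. If MI type is prognostic, these tests are slightly conservative and the hazard ratios slightly attenuated. Type I error is not inflated.

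Across the nine scenarios the stratum changed power by -0.1 to 2.7 points, and by less than 1 point in seven. These figures rest on the assumed two-fold hazard difference, the 50:50 split and the assumed centre spreads, and they use event counts of primary-endpoint size or somewhat below. A weaker MI-type effect would make the gain smaller still. The documents do not support a claim that omitting centre is an error. This is a free improvement of low priority.

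**What to change.** In SAP 12-21 and 23, stratify the Cox model by amikind_multi (STEMI/NSTEMI), and do the same for the log-rank test where one is specified (SAP 14-21 and 23). Leave the confirmatory primary test unchanged. Because the SAP authors were unblinded, record that the factor is the one fixed for the primary in SAP 2.0 and report the unstratified results alongside.

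A supportive analysis with centres pooled or grouped by country is optional. If one is added, state the pooling rule in advance.

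The cost is one strata term per endpoint and a short SAP amendment. The variable is already collected at enrolment, so no new data are needed.
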